10.3. Withdrawal From the Use of Research Samples

A subject who withdraws from the study will have the following options regarding exploratory biomarker research samples:

- The collected (scavenged) sample(s) will be retained and used in accordance with the subject's parent(s)/caregiver(s)' original informed consent for exploratory biomarker research.
- The parent(s)/caregiver(s) may withdraw consent for exploratory biomarker research, in which case the exploratory biomarker research samples will be destroyed and no further testing will take place. To initiate the sample destruction process, the investigator must notify the sponsor study-site contact of withdrawal of consent for the research samples and to request sample destruction. The sponsor study-site contact will, in turn, contact the biomarker representative to execute sample destruction. If requested, the investigator will receive written confirmation from the sponsor that the samples have been destroyed.

Withdrawal From the Use of Samples in Future Research

The parent(s)/caregiver(s) may withdraw consent for use of samples for research (refer to Section 16.2.5, Long-term Retention of Samples for Additional Future Research). In such a case, samples will be destroyed after they are no longer needed for the clinical study. Details of the sample retention for research are presented in the main ICF.

11. STATISTICAL METHODS

Statistical analysis will be done by the sponsor or under the authority of the sponsor. A general description of the statistical methods to be used to analyze the efficacy and safety data is outlined below. Specific details will be provided in the statistical analysis plan (SAP). The SAP for the IDMC will be separate from the SAP for the final analysis. In addition, a separate SAP for the interim analyses will be prepared.

All subjects who are randomized, have an RSV infection confirmed by central laboratory assessment, and receive at least 1 dose of study drug will constitute the intent-to-treat (ITT) infected population (ITT-i). Treatment assignment for this population will be defined by randomization assignment. The ITT-i population will be used for all efficacy/virologic analyses.

The per-protocol population will be defined as all subjects included in the ITT-i population without protocol deviations that affect efficacy assessment. The per-protocol population of ITT-i subjects with a postbaseline value will be established during the blinded data review and may be

used to perform sensitivity analysis on the primary endpoint. A blinded data review will be performed before each formal interim analysis.

All subjects enrolled into the study who receive at least 1 dose of study drug will be included in the safety population. Subjects in this population will be defined by the drug actually received, not by randomization assignment. Any subject who receives a single dose of lumicitabine will thus be included in the lumicitabine arm and all subjects that receive only placebo will be included in the placebo arm. The safety population will be used for all safety analyses.

11.1. Subject Information

All demographic characteristics and other initial subject characteristics will be tabulated and analyzed descriptively. Treatment adherence to lumicitabine will be derived from the collected information.

11.2. Sample Size Determination

The primary hypothesis is a positive dose-response relationship of active treatment on the average RSV viral load AUC over 7 days, meaning that either the average AUC on the pooled active treatments is lower than on placebo, or the average AUC on the high active dose is lower than the average AUC on placebo using multiple contrast testing. On high dose, the hypothesis of the lumicitabine antiviral activity assumes a viral load reduction on the AUC of the log viral load over 7 days of at least 30% when compared to placebo in subjects with onset of symptoms ≤ 3 days and of at least 20% in subjects with onset of symptoms > 3 days. The antiviral activity on low dose is assumed to be 80% when compared to the antiviral activity on the high dose. The positive dose-response relationship assumes that dose regimens with higher exposure with respect to MD will have at least an equal or better effect on viral load. Therefore 2 contrasts will be tested at each of the interim analysis points and final analysis; a contrast with no difference between the 2 active regimens tested against placebo (high equal to low, better than placebo) and a contrast with a positive 'linear' dose-response relationship (high better than low, low better than placebo) with respect to active regimens (where the effect of the low dose is exactly in between that of placebo and the high dose regimen). With respect to multiple contrast testing, multiplicity (2 contrasts) will be controlled at the prespecified (interim) alpha level by calculating adjusted p-values from the simulated distribution of the maximum or maximum absolute value of a multivariate t random vector (ie, using the correlation between the contrasts to optimally control for alpha).¹⁹ Based on the observed data of other in-house studies, the estimated SD is assumed to be approximately 34% of the AUC for subjects treated with placebo and the SD is equal in each of the treatment regimens. The overall (family wise) type 1 error rate of 2.5% (1-sided) will be adjusted for multiple testing due to formal interim analyses using a Pocock alpha spending function with 3 sequential tests (2 interim, 1 final).¹⁵ Based on 10,000 simulations and using a general linear model with treatment regimen as fixed factors, and under the assumption that 40% of the recruited subjects have onset of symptoms ≤ 3 days, a sample size of 180 subjects randomized in a 1:1:1 ratio will offer approximately 97% power to detect a positive dose-response relationship using multiple contrast testing. With the second interim analysis planned after at least 120 subjects, there will be at least 80% power to detect a positive dose-response relationship at the time of this analysis.

These sample size calculations were done under the assumption that option A is selected. Under option B, using similar assumptions, the total power is somewhat lowered but still sufficient for the total sample size of 180 subjects.

11.3. Efficacy Analyses

Primary Endpoint

The primary endpoint in this study is RSV RNA \log_{10} viral load (measured by qRT-PCR assay in the mid-turbinate nasal swab specimens) AUC immediately prior to first dose of study drug (baseline) over 7 days. Mean \log_{10} viral load values over time will be analyzed using a restricted maximum likelihood-based repeated measures approach. Analyses will include the fixed, categorical effects of treatment, strata, visit, and treatment-by-visit interaction, as well as the continuous, fixed covariates of baseline \log_{10} viral load and baseline \log_{10} viral load by-visit interaction. An unstructured (co)variance structure will be used to model the within subject errors over time. The Kenward-Roger method will be used to approximate the degrees of freedom.¹⁶ The difference in the AUCs for active versus placebo will be derived using appropriate contrasts deriving least square mean differences, including the 95% 2-sided confidence intervals. For inferential purposes, p-values will be compared with significance levels controlling for the (family-wise) type 1 error rate. Details will be provided in the SAP that will be finalized before the first formal interim analysis.

Secondary Endpoints

For differences between treatment groups on qRT-PCR the same methods as for the primary endpoint will be used, using appropriate contrasts to estimate treatment differences between the various treatment groups by treatment day using nominal 95% confidence intervals.

The time to virus not detected is defined as the time from initiation of study treatment until the time at which it is observed that the virus is undetectable in an assessment and after which time no virus positive assessment follows. Subjects will be (right-)censored at the last time observation of a detectable viral load. Actual sample time will be used. Data will be analyzed using Kaplan-Meier plots and using an accelerated failure time model to estimate difference between treatments, adjusting for strata and baseline viral load. Other baseline covariates may be added when statistically significant. In case the accelerated failure time model provides a poor model fit, appropriate sensitivity analyses will be performed as detailed in the SAP.

The time to clinical stability is defined as the time from initiation of study treatment until the time at which the following criteria are met: return to pre-RSV infection status (hereafter referred to as “normalization”) of blood oxygen level (ie, no additional requirement of supplemental oxygen compared with pre-RSV infection status), normalization of oral feeding, normalization of respiratory rate, and normalization of heart rate. Normalization criteria will be specified in the SAP. Subjects for which no timepoint could be established (eg, withdrawal of informed consent before reaching the endpoint or no clinical stability at last observation) will be (right-)censored at the latest timepoint at which it could be established that clinical stability was not reached. The differences in time to clinical stability of active dose regimens versus placebo treatment will be estimated using a Cox proportional hazard model; as baseline covariates, stratification factors,

absence/presence of other viral or bacterial infections, and baseline \log_{10} viral load will be added. Treatment effect versus placebo will be reported, including 95% confidence intervals. In case the proportional hazards assumption is not satisfied, appropriate sensitivity analyses will be performed as detailed in the SAP.

Additionally, statistical modeling will be performed on the secondary endpoint of length of hospital stay, defined as the time from treatment initiation to hospital discharge in hours. Subjects for whom no timepoint could be established (eg, withdrawal of informed consent before reaching the endpoint) will be (right-)censored at the latest timepoint at which it could be established that the endpoint was not reached. The differences in length of hospital stay of active dose regimens versus placebo treatment will be estimated using the accelerated failure time model using appropriate contrasts; as baseline covariates stratification factors, absence/presence of other viral or bacterial infections, and baseline \log_{10} viral load will be added. Treatment effect versus placebo will be reported as acceleration factors including 95% confidence intervals. In case the model assumptions are not adequately met, appropriate sensitivity analyses will be performed as detailed in the SAP. For the secondary endpoint of length of hospital stay, defined as the time from study treatment initiation to readiness for discharge in hours, with readiness for discharge defined by the investigator, an analogous approach will be used. The length of hospital stay from admission to discharge and from admission to readiness for discharge (as defined by the investigator), measured in days, will be analyzed using an analogous approach. Analytical details will be provided in the SAP.

Analysis of the sequencing results of the L-gene or other genes (only if no mutations are seen in the L-gene) will be described in the SAP. Statistical analysis of the viral load, that may be generated with the plaque assay, will be described in the SAP.

Parent/Caregiver-reported Evaluation of Clinical Outcomes

Parent/caregiver-reported eCOA (PRESORS) will be descriptively summarized by treatment group and compared across treatment groups.

Clinician-reported Evaluation of Clinical Outcomes

Clinician-reported eCOA (PRESORS) will be descriptively summarized by treatment group and compared across treatment groups.

11.4. Pharmacokinetic Analyses

Population PK analysis of concentration-time data of JNJ-63549109 will be performed using nonlinear mixed-effects modeling. Data may be combined with those of other selected studies to support a relevant structural model. Available baseline subject characteristics (eg, demographics, laboratory variables, and race) will be tested as potential covariates affecting PK parameters. Details will be given in a popPK analysis plan and the key findings of the popPK analysis will be presented in the final clinical study report. The popPK report will be provided separately.

A snapshot date for PK samples to be analyzed for the planned interim analysis will be defined. Samples collected before this date will be analyzed for JNJ-63549109 and JNJ-64167896 and

included in the popPK analysis (for JNJ-63549109 only). Samples collected after the snapshot date will be analyzed at a later date, and may be included in a popPK reanalysis when they become available after interim analysis database lock.

Subjects will be excluded from the PK analysis if their data do not allow for accurate assessment of the PK (eg, incomplete administration of the study drug; missing information of dose and sampling times; concentration data not sufficient for PK parameter calculation).

All concentrations below the lowest quantifiable concentration or missing data will be labeled as such in the concentration database. All subjects and samples excluded from the analysis will be clearly documented in the popPK report. The estimated model parameters and individual post hoc exposure parameters (AUC, C_{max} , and C_{12h}) will be provided for each subject as appropriate. Baseline covariates (eg, body weight, age, sex, creatinine clearance, and race) may be included in the model, if relevant.

For each treatment regimen, descriptive statistics, including arithmetic mean, SD, coefficient of variation, median, minimum, and maximum will be calculated for all individual derived PK parameters including exposure information of JNJ-63549109.

11.5. Biomarker Analyses

Statistical approaches to explore correlations between clinical outcome and biomarkers vary and depend on the different data types of the applied technology platforms, as well as on the extent of observed differences among study subjects. Analyses may be conducted at the sponsor's discretion and reported separately from this study.

11.6. Pharmacokinetic/Pharmacodynamic Analyses

Selected efficacy and safety parameters will be subject to PK/PD analysis. JNJ-63549109 exposures will be evaluated as an independent variable, with selected efficacy and selected safety parameters considered as dependent variables. Various approaches, including graphical analysis, linear, nonlinear, and logistic regression methods may be utilized.

The key findings of the PK/PD analyses will be presented in the final clinical study report.

11.7. Medical Resource Utilization and Health Economics Analyses

Medical resource utilization and health economics will be descriptively summarized by treatment regimen and compared across treatment regimens.

11.8. Safety Analyses

Safety data will be presented descriptively. No statistical testing of safety data is planned. For safety, baseline is defined as the last assessment prior to the first intake of study drug.

Adverse Events

The verbatim terms used in the eCRF by investigators to identify AEs will be coded using the Medical Dictionary for Regulatory Activities. Treatment-emergent AEs are AEs with onset during the treatment phase or that are a consequence of a preexisting condition that has worsened since baseline. All reported AEs will be included in the analysis. For each AE, the percentage of

subjects who experience at least 1 occurrence of the given event will be summarized by treatment regimen. In addition, comparisons between treatment regimens will be provided if appropriate.

Summaries, listings, datasets, or subject narratives may be provided, as appropriate, for those subjects who die, who discontinue treatment due to an AE, or who experience a severe or an SAE.

Clinical Laboratory Tests

Laboratory data will be summarized by type of laboratory test. Reference ranges and markedly abnormal results (specified in the SAP) will be used in the summary of laboratory data. Descriptive statistics will be calculated for each laboratory analyte at baseline and for observed values and changes from baseline at each scheduled timepoint. Changes from baseline results will be presented in pre- versus posttreatment cross-tabulations (with classes for below, within, and above normal ranges). Frequency tabulations of the abnormalities will be made. A listing of subjects with any laboratory results outside the reference ranges will be provided. A listing of subjects with any markedly abnormal laboratory results will also be provided.

The laboratory abnormalities will be determined according to the criteria specified in the draft DMID pediatric toxicity tables (see [Attachment 1](#)) and in accordance with the normal ranges of the clinical laboratory if no gradings are available.

Electrocardiogram

The effects on cardiovascular variables will be evaluated by means of descriptive statistics and frequency tabulations. These tables will include observed values and changes from baseline at each scheduled timepoint (the predose ECG will be used as baseline). Frequency tabulations of the abnormalities will be made.

The ECG variables that will be analyzed are heart rate, PR interval, QRS interval, QT interval, and QTcF.^{12,14,19} The percentage of subjects with abnormalities as defined in [Attachment 2](#) will be tabulated.

Vital Signs/SpO₂

Descriptive statistics of body temperature, heart rate, respiratory rate, SBP, DBP, SpO₂, and changes from baseline will be summarized at each scheduled timepoint. For SpO₂ an overview will be presented for the number of subjects (proportion) requiring supplemental oxygen. The percentage of subjects with values beyond clinically important limits, as judged by the investigator, will be summarized.

Physical Examination

Physical examination findings will be summarized at each scheduled timepoint. Descriptive statistics will be calculated at baseline and for observed values and changes from baseline at each scheduled timepoint. Frequency tabulations of the abnormalities will be made.

11.9. Interim Analysis

An Interim Analysis Committee will be responsible for performing the formal interim analysis and will consist of sponsor personnel who are not otherwise involved in the study. The IDMC will review the data and make recommendations to the Sponsor Committee, which will be responsible for identifying appropriate actions based on the recommendations of the IDMC.

Two types of interim analyses are distinguished: formal interim analysis and interim analyses performed by the IDMC only. The IDMC is described in Section 11.10, Independent Data Monitoring Committee, and Section 3.1, Overview of Study Design. At any formal interim analysis, the IDMC will also perform a data review.

The Interim Analysis Committee will be responsible for performing any formal interim analysis and will consist of sponsor personnel who are not otherwise involved in study activities. The first formal interim analysis will be performed when 36 subjects with ≤ 3 days of RSV symptoms have completed treatment or when 90 subjects with >3 to ≤ 5 days of RSV symptoms have been enrolled and have completed treatment. The second interim analysis may be performed at the discretion of the sponsor when at least 120 subjects have completed treatment (or at least 60 subjects with ≤ 3 days of RSV symptoms), which may allow an analysis at the end of a season.

The following situations will be considered based on the results of any formal interim analysis: that the study is considered futile; that superiority can be concluded; that subjects with >3 to ≤ 5 days of RSV symptoms at randomization may not achieve benefit (which may also be limited to ≤ 4 days of onset to symptoms); that the treatment duration needs to be increased to up to 10 days; or that the study should continue unchanged. In the case of the (unbinding) futility boundary or the superiority boundary being crossed, the IDMC may recommend early termination to the Sponsor Committee. If early superiority on the primary endpoint can be established, the study may be continued in order to accumulate data to allow the selection of the dose regimen or further substantiate the benefit-risk profile in this population; in this case the randomization ratio of active to placebo treatment may be altered for example, if dose selection is evident from the dose-response analysis, subjects randomized to active treatment may all receive the optimal dose. Alternative randomization ratios can be endorsed by the IDMC and implemented by the Sponsor Committee for Option A are 1:2:0, 1:0:2, 1:2:2, and 2:1:3 for the placebo, low dose, and high dose, respectively. The IDMC may recommend that the randomization ratios for Option B be changed.

Results of the formal interim analyses can be used in interactions with Health Authorities.

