3.1.1. Option A

Hospitalized infants and children who are infected with RSV will be randomly assigned to a treatment regimen in this study, with 60 subjects planned per regimen. At least 120 subjects are planned to be enrolled up to a maximum of 180 subjects. An effort will be made to enroll at least 90 subjects aged between 28 days and 24 months and at least 12 subjects aged between 24 and 36 months. The number of subjects with comorbidities will be limited to 20%; additional comorbid subjects aged between 24 and 36 months may be allowed to enroll if the 20% threshold is reached before 12 subjects aged between 24 and 36 months are enrolled into the study.

Subjects will be randomized in a 1:1:1 ratio to Regimen A, B, or C:

- Regimen A (low-dose lumicitabine): a single 40 mg/kg LD (Dose 1) followed by nine 20 mg/kg MDs (Doses 2 to 10) of lumicitabine, administered twice daily.
- Regimen B (high-dose lumicitabine): a single 60 mg/kg LD (Dose 1) followed by nine 40 mg/kg MDs (Doses 2 to 10) of lumicitabine, administered twice daily.

- Regimen C (placebo): those randomized to a placebo regimen are subsequently randomized in a 1:1 ratio (to match volumes) to either:
 - A single 40 mg/kg placebo LD (Dose 1) followed by nine 20 mg/kg MDs (Doses 2 to 10), administered twice daily.
 - A single 60 mg/kg placebo LD (Dose 1) followed by nine 40 mg/kg placebo MDs (Doses 2 to 10), administered twice daily.

An IDMC (refer to Section 11.10, Independent Data Monitoring Committee, for details) will review the safety and PK data once the first 12 subjects and 30 subjects have completed treatment (Day 5/6) to assess if enrollment of additional subjects may safely continue in each arm. After at least 9 subjects have completed treatment with the 60 mg/kg LD/40 mg/kg MD lumicitabine regimen, the IDMC may recommend that sparse PK sampling be used for the other subjects. Subject recruitment and enrollment may continue while the data are being reviewed.

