Up to 2 formal interim analyses may be performed during the study. The first interim analysis will be performed once 36 subjects with ≤ 3 days of RSV symptoms have completed treatment (Day 5/6) or once 90 subjects with >3 to ≤ 5 days of RSV symptoms have been enrolled and have completed treatment. The following situations will be considered based on the results at this stage: that the study is considered futile; that superiority can be concluded; that subjects with >3 to ≤ 5 days of RSV symptoms at randomization may not achieve benefit (which may also be limited to ≤ 4 days of onset to symptoms); or that the study can continue unchanged. The treatment regimen may be modified after the first interim analysis, including increasing the treatment duration up to 10 days. After this analysis, randomization to 1 of the lumicitabine doses may be discontinued, the randomization ratio may change, and the study may not continue in subjects with >3 to ≤ 5 days of RSV symptoms at randomization. The second interim analysis may be performed at the discretion of the sponsor once at least 120 subjects have completed treatment (Day 5/6) (or at least 60 subjects with ≤ 3 days of RSV symptoms). The following situations will be considered based on the results at this stage: that the study is considered futile; that superiority can be concluded; or that the study can continue unchanged. Based on the recommendations of the IDMC following these interim analyses/reviews of PK, efficacy, and safety data, changes to randomization ratios in the treatment arms or an increase in treatment duration to 10 days may be implemented.

The design for Option A is provided in [Figure 2](#).

Figure 2: Schematic Study Overview: Option A

Abbreviations: LD: loading dose; MD: maintenance dose; RSV: respiratory syncytial virus.

a. Subjects randomized to placebo will be subsequently randomized in a 1:1 ratio to the placebo regimen matching Regimen A or Regimen B.

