 - A single placebo LD (Dose 1) followed by nine MDs (Doses 2 to 10) of placebo matching Regimen 2, administered twice daily.

An IDMC will review the safety and PK data from Cohort 2 once at least 9 subjects in Cohort 2 have completed treatment (Day 5/6) with the active lumicitabine Regimen 2. Subject recruitment and enrollment for Cohort 2 may continue while the data are being reviewed.

A third dose may be evaluated, upon IDMC recommendation, based on the emerging safety and PK profile. Subjects will be enrolled into Cohort 3 and randomized in a 1:3:2 ratio to lumicitabine Regimen 1, lumicitabine Regimen 3, or placebo:

- Lumicitabine Regimen 1: a single 40 mg/kg LD followed by nine 20 mg/kg MDs of lumicitabine, administered twice daily.
- Lumicitabine Regimen 3: a single LD followed by 9 MDs of lumicitabine Regimen 3, administered twice daily. The IDMC will provide a dose recommendation for the lumicitabine Regimen 3.
- Placebo: Those randomized to a placebo regimen are subsequently randomized in a 1:3 ratio (to match volumes) to either:
 - A single 40 mg/kg placebo LD (Dose 1) followed by nine 20 mg/kg MDs (Doses 2 to 10) of placebo, administered twice daily.
 - A single placebo LD (Dose 1) followed by nine MDs (Doses 2 to 10) of placebo matching Regimen 3, administered twice daily.

An IDMC will review safety and PK data from Cohort 3 once 9 subjects in that cohort have completed treatment (Day 5/6) with the active lumicitabine Regimen 3, at which stage the IDMC will select either lumicitabine Regimen 2 or lumicitabine Regimen 3 to be used with placebo and lumicitabine Regimen 1 for the remainder of the study. Depending on the selected doses, other randomization schemes may be selected for the remainder of the study. Subject recruitment and enrollment for Cohort 3 may continue while the data are being reviewed. Subjects will continue to be enrolled and treated in Cohort 2 up to a maximum of 180 subjects if a third dose regimen is not evaluated.

The sponsor/IDMC may recommend that the cohort regimens be adjusted or removed, given the active nature of the development program and the ongoing assessment of all the available data.

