2. GENERAL ANALYSIS DEFINITIONS

2.1. Visit Windows and Phase Definition

Figure 1: Schematic Study Overview: Option A

Abbreviations: LD: loading dose; MD: maintenance dose; RSV: respiratory syncytial virus.

- a. Subjects randomized to placebo will be subsequently randomized in a 1:1 ratio to the placebo regimen matching Regimen A or Regimen B.

Phases will be constructed as follows:

Trial phase	Start date	End date
Pre-screening	Date time of first assessment, taken as part of standard of care within 84 hours* prior to randomization	1 minute before start of screening phase
Screening	00:00 of the date of signing the informed consent	1 minute before the first study medication intake
Treatment	Date time of first study medication intake	Date time of last investigational medication intake + 72 hours
Follow-up	End of Treatment phase + 1 minute	Trial termination date (date of last contact) with timestamp 23:59.

*In order to account for “approximately” 72 hours prior to randomization

The last phase, whichever it is for a subject, always ends on 23:59 of the day of trial termination (last contact) in study 64041575RSV2004. Note a subject can volunteer for long-term follow-up, in this case the subject will be enrolled in study 64041575RSV2002.

Assessments will be assigned to phases based on their date time, seconds will be ignored. If the day part of the start date of the assessment is present but the time part is missing, the assessment will be allocated as if it started at 00:00h on the day of the assessment (unless for Adverse Events see details in section 6.1.1). If the day part of the end date of the assessment is present but the time part is missing, no formal imputation will be done, but these rules will only be applied in order to be able to allocate assessments to phases. The assessment will be allocated as if it happened at 23:59h on the day of the assessment.

As subjects do not always adhere to the protocol visit schedule, the following rules are applied to assign actual visits to analysis visits. Listed below are the visit windows and the target days for each visit.

All visits (regardless the investigated parameter) will be allocated to analysis visits based on the day relative to the start of study medication:

Target Day	Analysis visit (numeric version)	Analysis visit	Day Interval
$-\infty$	-1	Screening	≤ 1 ¹
1	0	Baseline	≤ 1 ²
1	1	Day 1	[1] ³
2	2	Day 2	[2]
3	3	Day 3	[3]
4	4	Day 4	[4]
5	5	Day 5	[5]
6	6	Day 6	[6]
7	7	Day 7	[7,9]

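### Option A states only a 1:1 placebo volume split and gives no rule to re-match it when the allocation ratio changes; if kept, volume identifies half of new placebo subjects under 1:2:0 or 1:0:2

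*Protocol*

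**What the plan says.** Protocol 3.1.1 sets the starting allocation: "Subjects will be randomized in a 1:1:1 ratio to Regimen A, B, or C". Directly below, for the placebo regimen, it adds: "those randomized to a placebo regimen are subsequently randomized in a 1:1 ratio (to match volumes) to either" of the two volume schedules. The Synopsis and SAP 1.2.1 carry the same text. The footnote to the design figure, in Protocol 3.1.1 and again in SAP 2.1, repeats it: "Subjects randomized to placebo will be subsequently randomized in a 1:1 ratio to the placebo regimen matching Regimen A or Regimen B". No other placebo split is given for Option A, and no condition is attached to this one.

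Protocol 11.9 and SAP 3.1 then list the permitted alternatives, in the order placebo, low dose, high dose: "Alternative randomization ratios can be endorsed by the IDMC and implemented by the Sponsor Committee for Option A are 1:2:0, 1:0:2, 1:2:2, and 2:1:3". They introduce the list in the context of continuing after early superiority. Protocol 3.1.1 is broader. After the first interim analysis, "randomization to 1 of the lumicitabine doses may be discontinued, the randomization ratio may change", with no requirement that superiority has been shown. Protocol 11.10 and SAP 3.2 say that ratio changes are notified in writing to investigators, health authorities and ethics committees, and may take effect without a protocol amendment.

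Option B treats the split differently. In Cohort 3, where low dose, high dose and placebo are allocated 1:3:2, placebo subjects are "subsequently randomized in a 1:3 ratio (to match volumes) to either" of the two volumes (Protocol 3.1.2).

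**The concern.** Protocol Section 6 gives one suspension strength, 60 mg/mL, so volume per kg follows the mg/kg dose and the two regimens can be told apart by anyone who prepares or gives a dose. The blind therefore depends on placebo being spread over the two volumes in the same proportion as the active doses. A 1:1 split achieves this only while the low and high doses are allocated equally, and three of the four alternatives are unequal. An investigator who has been told the ratio and sees the volume could then identify some placebo subjects, or revise the odds for others.

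The outcomes at stake rest on judgement: readiness for discharge, whether respiratory rate and heart rate are normal for the child (both feed time to clinical stability), the clinician PRESORS, and adverse event causality. Protocol 11.9 gives dose selection and further support for the benefit-risk profile as reasons to continue after early superiority, and such data bear on both.

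**Working it through.** **Inputs.** Strength 60 mg/mL (Protocol Section 6). Low regimen 40 mg/kg loading and 20 mg/kg maintenance; high regimen 60 and 40 mg/kg (Protocol 3.1.1). Starting allocation 1:1:1 and placebo split 1:1 (Protocol 3.1.1). Alternatives 1:2:0, 1:0:2, 1:2:2 and 2:1:3, as placebo:low:high (Protocol 11.9). Option B Cohort 3 allocation 1:3:2 as low:high:placebo, placebo split 1:3 (Protocol 3.1.2).

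**Can the volumes be told apart?** Loading dose: 40/60 = 0.67 against 60/60 = 1.00 mL/kg. Maintenance: 20/60 = 0.33 against 40/60 = 0.67 mL/kg. For an assumed 8 kg child this is 5.3 against 8.0 mL, then 2.7 against 5.3 mL.

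**Formula.** For allocation p:l:h and a 1:1 placebo split:

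P(placebo | low volume) = (p/2) / (p/2 + l)

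P(placebo | high volume) = (p/2) / (p/2 + h)

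Volume carries no information when both equal the overall placebo share, p/(p + l + h).

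**The plan's own splits.** Option A at 1:1:1: 0.5/(0.5 + 1) = 1/3 at each volume, equal to the placebo share. Option B Cohort 3, rewritten as placebo:low:high, is 2:1:3. With its 1:3 split the placebo weights are 0.5 low and 1.5 high, giving 0.5/(0.5 + 1) = 1/3 and 1.5/(1.5 + 3) = 1/3. Both stated splits do what they are meant to do.

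**The alternatives with the 1:1 split kept.**

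| Placebo:low:high | Placebo share | P(placebo, low volume) | P(placebo, high volume) |
|---|---|---|---|
| 1:2:0 | 1/3 | 0.5/2.5 = 20% | 0.5/0.5 = 100% |
| 1:0:2 | 1/3 | 0.5/0.5 = 100% | 0.5/2.5 = 20% |
| 1:2:2 | 1/5 | 0.5/2.5 = 20% | 0.5/2.5 = 20% |
| 2:1:3 | 1/3 | 1/2 = 50% | 1/4 = 25% |

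Under 1:2:0 or 1:0:2, half of the new placebo subjects receive a volume that no active subject receives: 0.5/3 = 1/6 of new subjects. For everyone at the other volume, placebo becomes less likely (20% against 33%). Under 2:1:3, the low volume goes to 1/2 of placebo and 1/4 of active subjects, a likelihood ratio of 2.

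**Scale.** If 40% of subjects have symptoms for 3 days or less (Protocol 11.2), 36 such subjects are reached at about 36/0.40 = 90 enrolled. With a planned total of 120 to 180, that leaves 30 to 90 subjects. A change to 1:2:0 or 1:0:2 at that point would identify 30/6 = 5 to 90/6 = 15 children, fewer if enrolment runs on during the analysis.

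**The alternatives with a matched split.** 1:2:0 uses the low volume only and 1:0:2 the high volume only, each giving 1/3. 1:2:2 with a 1:1 split gives 1/5 at both volumes. 2:1:3 with a 1:3 split gives 1/3 at both. Each equals the overall placebo share.

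**The case against.** The strongest reply is that the 1:1 split belongs to the starting scheme. It sits under the 1:1:1 sentence, its stated purpose is to match volumes, and nothing says that it survives a ratio change. Option B suggests that the sponsor would re-match: one placebo volume in Cohort 1, 1:1 in Cohort 2, 1:3 in Cohort 3, and a figure footnote that ties placebo to whichever active regimens are in use. Re-matching might also be set out in the IDMC Charter, the IWRS specification or the pharmacy manual, which are not part of these documents. This stands to the extent that a reader might infer the split is fixed at 1:1, and the documents do not say so. The defect is a missing rule. It still matters because 1:1 is the only Option A split written down, and a ratio change needs no amendment that would force someone to revisit it.

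Three further limits stand. Under 2:1:3 volume shifts the odds but does not come close to revealing placebo. The primary endpoint is a central-laboratory qRT-PCR result. Subjects randomised before a change are unaffected.

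A reader might also infer that parents, who dose, swab and complete the diary at home after discharge, would be unblinded. Inferring placebo needs knowledge of the allocation in force, and Protocol 11.10 does not list parents among those told.

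Protocol Section 5 promises careful handling of preparation and accountability data, but this does not hide the volume from the staff who give the dose.

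**Conclusion.** The gap is real and should be closed before any ratio change. It rests on three conditions: a change to an alternative other than 1:2:2, the 1:1 split being kept, and the investigator both knowing the ratio and seeing the volume. The documents provide for the first and for the investigator being told; they are silent on the second. If all three hold, placebo is certain for half of the placebo subjects randomised after a move to 1:2:0 or 1:0:2. Under 2:1:3 the leak is moderate. The consequence is potential bias in investigator-judged secondary outcomes and in adverse event causality for those subjects, with much less reach into the primary analysis. The documents do not support saying that the blind will fail, only that the plan as written does not prevent it.

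**What to change.** In Protocol 3.1.1 and 11.9, mirrored in SAP 1.2.1 and 3.1, state that placebo subjects are sub-randomised to volume in the same low:high ratio as the active arms in force. Spell out the result: 1:1 under 1:1:1 and 1:2:2; low volume only under 1:2:0; high volume only under 1:0:2; 1:3 under 2:1:3, as Option B Cohort 3 already has it. Amend the design-figure footnotes in both documents to agree. Prepare the matching IWRS lists in advance, so that a ratio change and its placebo split take effect together. The cost is one sentence in each place and a set of lists for every permitted ratio; no subjects or assessments are added.
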